 - h. Performing / conducting tests, procedures, interventions, questionnaires: [name], [name], [name]
 - i. Completing study data forms: [name], [name]
 - j. Managing study database: [name], [name]

L. Assessment of Subject Safety and Development of a Data and Safety Monitoring Plan

1. Elements of the plan include:
 - a. Persons/groups who will review the data (study team; independent safety monitor, data monitoring committee or formal DSMB): PI and study team
 - b. Data/events that will be reviewed: n/a
 - c. Frequency of review: n/a
 - d. Types of analyses to be performed: n/a
 - e. Safety-related triggers that would cause the PI to stop or alter the study: n/a
2. n/a – non-interventional study, no anticipated adverse events related to the study
3. n/a – non-interventional study, no anticipated adverse events related to the study

III. Subject Participation

A. Recruitment:

1. Subjects will be recruited from the ADORE GAINS study cohort if they agreed to future contact on the informed consent form at the time of consent for that study.
2. Study coordinators and graduate research assistants will contact potential participants by phone. The study will be explained using the recruitment script (pending IRB approval).
3. n/a – no advertisements or flyers will be used for recruitment

4. The recruitment diagram and recruitment postcard will be sent to potential participants who express interest when spoken to on the phone and agree to have the materials sent electronically. These handouts are intended to provide a simple, visual overview of what the entails. They will be accompanied by the more detailed verbal explanation provided by the study team via phone.

B. Screening Interview/questionnaire: The general health screener will be sent to parent to complete. This has questions to assess MRI safety and if the child has been diagnosed with autism.

C. Informed consent process and timing of obtaining of consent

1. [name], [name] will be in charge of obtaining written consent.
2. The consent process will occur via phone or in a private room with only approved study personnel present. The electronic consent form is structured in different sections including study purpose, study procedures, risks and benefits, additional information (cost, payment, funding, voluntary reminder), privacy protection, stopping the study, and lastly the consent page with signature fields. Each section is a different page, so the interviewee has to advance to the next section. The interviewer will verbally explain each section to the potential participant. By structuring the form in sections, participants receive small amounts of information at a time making it easier to understand. It also creates a natural pause after each section, at which time the interviewer will give the participant the opportunity to ask any questions. After the consent interview, participants will be given the opportunity to think about the decision and discuss privately with their spouse/partner if applicable. If consent interview occurs in-person, the study team member will step out of the room should they want time to think/discuss privately. If the consent occurs via phone, a second phone call will be scheduled to actually sign the consent if they choose to do so.
3. All subjects will be minors, therefore a legal guardian will give informed consent for all subjects.

D. Alternatives to Participation: As stated in the consent form, a parent can choose not to have their child participate.

E. Costs to Subjects: n/a – all study tests and procedures will be provided by the study. No study-related procedures will be billed to insurance. A subject's health insurance status will not impact their ability to participate.

F. How new information will be conveyed to the study subject and how it will be documented: New information will be conveyed to the study subject in writing, via a letter. A dated copy of the letter will be kept in their research record to document that the information was provided. Reconsent will occur if required by the IRB.

G. Payment, including a prorated plan for payment: Subjects will receive \$100 per visit attended. The reimbursement will be requested to the ClinCard after each study visit is completed. If a subject chooses to withdraw, they will only receive compensation for the study visit(s) completed. Reimbursement for travel expenses may be available, but will need

to be pre-approved by the PI.

H. Payment for a research-related injury: Treatment for research-related injury will be provided at usual charge. Claims will be submitted to the subject's health insurance policy, government program, or other third party. The subject will be billed for any costs not covered by the insurance.

IV. Data Collection and Protection

A. Data Management and Security:

1. In addition to the PI, Co-I, and IRB-approved study team members, data monitors and auditors from the IRB and regulatory authorities will have access to study data.
2. To maintain confidentiality, subjects will be given a non-identifiable study ID number. Research records containing identifiable information will be kept in [name] locked research laboratory. All study records will be retained for 25 years, per university policy for pediatric studies.
3. Subjects will be identified by their study ID number.
4. The study coordinators will maintain and have access to the information that links the subject's identity to their study ID number.
5. Data will be linked to the subject using their assigned study ID number.
6. Data will be stored on the KUMC RedCap server and university P-drive. Only IRB-approved study team members will have access to the data.
7. iPads may be used for electronic data entry during study visits. All data collected via iPad will be entered into RedCap and stored on the KUMC RedCap server. A study specific iPad will be used to take and temporarily save photos of children during the DXA scan. The iPad is passcode protected and only approved members of the study team have access. After each visit, photos will be saved to the university P-drive and deleted from the iPad. If the parent consents yes to the future use of photos, photos will be kept on the P-drive for possible future use in presentations and publications of the research in accordance with the optional multimedia consent and KUMC multimedia authorization form. If the parent consents no to the future use of photos, all photos of the participant will be deleted after sharing them with the participant as a memento of their participation.
8. n/a – no identifiable data will be sent outside KUMC

B. Sample / Specimen Collection: n/a – no samples will be collected

C. Tissue Banking Considerations: n/a – no samples will be collected, therefore no samples will be available to bank

D. Procedures to protect subject confidentiality: There is no appreciable risk of loss of confidentiality. Subjects will be made aware of persons who may see their protected health information in the informed consent document and may choose not to enroll in the study based on the information provided them in accord with 2003 HIPAA regulations. The patient's confidentiality will be maintained and will not be made publicly available to the extent permitted by the applicable laws and regulations.

E. Quality Assurance / Monitoring

1. All data entry will be verified by a second study team member using the original source document to ensure data are accurate, consistent, complete and reliable.
2. n/a – no plans to have ongoing third-party monitoring

V. Data Analysis and Reporting

A. Statistical and Data Analysis: The data analysis plan for each primary aim is described below. There are no planned interim analyses.

1. **Aim 1 analysis:** Determine the relationship between added sugars (grams and % calories) intake during pregnancy and infancy/toddlerhood (birth to 24 months) on brain structure and function. Brain structure will be quantified as brain volume in Freesurfer. Based on prior studies, we will examine the Pearson correlation between hippocampal brain volume and added sugars intake during pregnancy and infancy/toddlerhood. Exploratory analyses will examine correlations with added sugars intake and brain volume in inhibitory control brain regions (i.e., dorsal anterior cortex) and reward related regions (i.e., ventromedial prefrontal cortex). Brain function will be quantified as resting state functional connectivity within the default mode network which includes prefrontal and parietal regions as well as the attention and salience networks. Pearson correlations will examine the relationship between functional connectivity metrics and added sugars intake. Brain function during the EEG Food Go/NoGo task will be quantified as the amplitude of the P3 and N2 components and correlations will examine the relationship between P3/N2 amplitudes and added sugars. Analyses will be corrected for multiple comparisons using a Bonferroni correction.
2. **Aim 2 analysis:** Determine the relationship between fructose (grams and % calories) consumption during pregnancy and infancy/toddlerhood (birth to 24 months) on brain structure and function. As in Aim 1 analyses, brain structure will be quantified as Freesurfer volumes, brain function will be quantified as resting state connectivity, and brain activation during the EEG Food Go/NoGo Task. Correlations will be used to examine the relationship between brain measures and fructose consumption.

B. Outcome: We hypothesize that added sugars and fructose intake will be negatively related to brain structure (hippocampal volume) and function (resting state functional connectivity and P3 amplitude). The strength of the correlations and level of significance will determine if there is a relationship between variables being tested.

C. Study results to participants: Study participants will be informed of the overall study results via a letter, which will be mailed after the study and analysis is complete. Participants will not be given their individual results from study procedures; however, this information may be made available upon request, with approval by the PI.

D. Publication Plan: The present study is a pilot. This project was submitted as a June 2022 R01 and received positive reviews. It will be resubmitted in November 2022 with the hope of receiving R01 funding to extend the study to the entire ADORE GAINS cohort. We hope by getting more participants to complete the cognitive tests and body composition measurements that we will have a large enough sample to publish results relating to those

measurements. Any publications would further support the R01 application.

VI. Literature Cited

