In 7-11-year-old children⁴⁸, increased intake of fructose and glucose was associated with increased right hippocampal CA2/3 subfield volume, and increased fructose intake was associated with mean diffusivity in the right cingulate-prefrontal cortex connections. This suggests an impact on hippocampal structure related to an increase in hippocampal inflammation. In the Project Viva cohort⁵⁵, greater maternal prenatal intake of SSB was related to poorer offspring global intelligence. Greater maternal prenatal added sugars consumption was also related to lower newborn gray matter at 3 weeks old, including areas for later cognitive functioning³⁴, suggesting an impact on formation of dendrites and synapses. This cohort was tested again at 24 months using the Bayley-III Scales of Infant Development⁵⁶. Greater maternal SSB intake was related to lower scores on the Bayley-III. These data provide evidence for a relationship between maternal added sugars intake and the brain structures that are the foundation for future cognitive development.

C. Rationale

1. As described above, there is a growing body of evidence to suggest that excess added sugar intake negatively affects cognition.
2. The innovation for this proposal involves a shift with respect to the theoretical approach around the relationship between cognition and nutrition. *While the impact of key nutrient deficiencies on cognition is well documented, the relationship between excess intake (i.e., added sugars) and cognitive development has not been previously studied.* Further, data are lacking on exposure timing relative to the impact on cognition and brain

development. This proposal will investigate three time periods that are well established windows of brain development that are sensitive to nutrient exposures: the prenatal, infancy, and toddlerhood time periods.

3. n/a – this study is not designed to improve the diagnosis or treatment of a disease

II. Research Plan and Design

A. Study Objectives: This purpose of this study is to fill a gap in the literature by providing an understanding of the relationship between added sugars and fructose intake during sensitive windows to brain structure and function. This project is unique because we can determine the effect of added sugars during three different times: pregnancy, infancy, and toddlerhood.

Primary Aims:

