Aim 1: Determine the relationship between added sugars (% calories) intake during pregnancy and infancy/toddlerhood (birth to 24 months) on brain structure and function.

Aim 2: Determine the relationship between fructose (% calories) consumption during pregnancy and infancy/toddlerhood (birth to 24 months) on brain structure and function.

Secondary Aims:

Secondary Aim 1: Determine the relationship between added sugars (% calories) intake during pregnancy and infancy/toddlerhood (birth to 24 months) on cognition.

B. Study Type and Design: This is a non-interventional, observational study.

Added sugar intake during pregnancy will be assessed using dietary data collected between 12-20 wks gestation using the National Cancer institute (NCI) DHQ-II food frequency questionnaire (FFQ) or three 24-hour dietary recalls.

Offspring dietary intake was collected at 2 weeks and at 6, 12, and 24 months by one multiple-pass 24-hour dietary recall administered to the child's caregiver and collected by trained research staff.

For the present study, we will collect three total dietary recalls: two weekday and one on the weekend.

Brain structure and function will be measured using MRI and EEG assessments. Cognition will be measured using dimensional change card sort task and Peabody picture vocabulary test.

C. Sample size, statistical methods, and power calculation

1. n/a – randomization will not be used
2. n/a – study will not be blinded
3. The present study is pilot. The planned sample size is 45 subjects.

D. Subject Criteria (See Vulnerable Populations appendix, if applicable): Participants who were previously enrolled in the ADORE GAINS study will be invited to participate in the present study when they are 5-6 years old. Participants will be both male and female and English or Spanish speaking.

1. Inclusion criteria: Participated in ADORE GAINS. Age 5-6.
2. Exclusion criteria: children who have received an autism diagnosis (per parent report)
3. Withdrawal/Termination criteria: n/a

4. Subjects may enter another research study while participating in this research study, as this study is observational only.

E. Specific methods and techniques used throughout the study

1. Laboratory tests: n/a
2. Study Procedures:

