Dimensional Change Card Sort (DCCS) task. This test is based on the basic paradigms of discrimination learning^{65,66}, which was a focus of our laboratory's research program during the 1990s^{67,68}. This particular task is administered according to the protocol published by⁶⁹, and has also been used in other nutritional studies, as well as in our research program on the development of attention in preschoolers⁷⁰. Essentially, participants are presented with stimuli that can be sorted on various dimensions (e.g., shape or color). They are asked to sort the stimuli on one dimension (thus providing a measure of performance on that ability) but then are asked to reverse (i.e., "switch") the rule. At that point, they must inhibit the previously activated rule in order to perform correctly under the new rules. For this particular task, children are presented a game in which they must sort 7 "red bunny" cards and 7 "blue car" cards into one of two boxes. One box is "labeled" with a red car and the other with a blue bunny. The child is asked to play either the "color game," with red bunnies sorted (face down) into the "red car" box; blue cars sorted (face down) into the "blue bunny" box; or they are asked to play the "shape game," with blue cars sorted (face down) into the "red car" box and red bunnies sorted (face down) into the "blue bunny" box. The protocol is to administer two practice trials, and then 6 trials with varying levels of support as needed (i.e., instructions may be repeated, or cards may be identified as a scaffold for the production of strategies) although the answers are never given to the child. If children perform 5 out of 6 trials correctly, the game is switched to the opposite (i.e., shape-to-color or color-to-shape). Should the child successfully negotiates the switch, the task would proceed with the "border version" of the task, where half of 12 sorting cards have a black border around the picture, and the child is asked to play "color game" when the card has a black border and "shape game" when it does not; here, there are 12 trials, but no game-switch phase. Correct responses are recorded for each phase, and performance is also qualitative characterized as 0 (fail pre-switch phase), 1 (pass pre-switch, fail post-switch), 2 (pass the pre- and post-switch phases, but fail border phase), and 3 (pass all phases). The DCCS task will take approximately 15 minutes.

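### Does the lack of a written analysis for Secondary Aim 1 (added sugars and cognition) call for a change to the plan?

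*Combined protocol and SAP*

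**What the plan says.** Protocol section II.A lists "Secondary Aim 1: Determine the relationship between added sugars (% calories) intake during pregnancy and infancy/toddlerhood (birth to 24 months) on cognition". Section II.B adds "Cognition will be measured using dimensional change card sort task and Peabody picture vocabulary test". Section II.E.2 describes both tests. The PPVT-4 gives a standard score with mean 100 and SD 15. For the card sort, "Correct responses are recorded for each phase, and performance is also qualitative characterized as 0 (fail pre-switch phase", and so on up to 3 for passing every phase.

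Section V.A limits itself at the outset: "The data analysis plan for each primary aim is described below". Only Aims 1 and 2 follow, with correlations on MRI and EEG measures. Bonferroni correction is stated once, in the Aim 1 paragraph. Section V.B gives a hypothesis on brain outcomes only, then a general sentence: "The strength of the correlations and level of significance will determine if there is a relationship between variables being tested". Section II.C calls the study a pilot of 45 children and states no power, alpha or effect size.

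On intake, II.A says "we can determine the effect of added sugars during three different times: pregnancy, infancy, and toddlerhood", while the aims join infancy and toddlerhood into one period. Section II.B reports that "Offspring dietary intake was collected at 2 weeks and at 6, 12, and 24 months by one multiple-pass 24-hour dietary recall". Section V.D says of the cognitive results: "We hope by getting more participants to complete the cognitive tests and body composition measurements that we will have a large enough sample to publish".

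**The concern.** An aim has two outcome measures and a possible publication, but no named test, score or family of tests. The text of section V runs without a break, so removed pages do not explain the gap.

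Three things look open:

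- **Intake windows.** They could be two, three, or one for each recall age.
- **Card-sort variable.** Phase counts and a 0-3 category are both recorded. The phases are gated, so a child who fails the switch has no border-phase count. An analysis of that count alone would leave out the weakest performers.
- **Multiplicity.** No family is named, and nothing says whether Bonferroni reaches this aim.

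If these were settled after the cognition data had been seen, a reader could not tell a planned correlation from a selected one.

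**Working it through.** The plan has no figure to reproduce here: 45 is given without alpha, power or effect size. The check is therefore whether each open item has a sensible filling in the documents, and what that filling costs.

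**Step 1. What is already fixed, and what fills the rest**

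| Item | In the documents | Filling |
|---|---|---|
| Intake unit | % calories (II.A) | Fixed. Grams appear in V.A for Aims 1 and 2, not in this aim |
| Period | Pregnancy; birth to 24 months (II.A) | Two windows, as Aim 1 is worded in V.A |
| PPVT-4 | Standard score (II.E.2) | Fixed |
| Card sort | Phase counts and 0-3 category (II.E.2) | 0-3 category: failing the first phase scores 0, so no tested child drops out |
| Method | Correlation (V.A) | Same |
| Multiplicity | Bonferroni (V.A, Aim 1) | Same |

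Nowhere does the plan propose analysing the border count alone, so the loss of weaker performers is a possible misuse and not a stated method.

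**Step 2. Which gaps belong to this aim**

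The Aim 1 paragraph uses the same pregnancy and infancy/toddlerhood wording, gives no rule for combining the four recalls, and names no Bonferroni family. Those two gaps run through the whole study. Only the choice of card-sort score is specific to cognition.

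**Step 3. Size**

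Inputs: N = 45 (II.C), so df = 43; alpha 0.05 two-sided (assumed, as none is stated); k = windows × scores.

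- Critical |r| = t / √(df + t²), with t at alpha/k.
- Detectable |r| at 80% power = tanh[(z_alpha + z_power) / √(N − 3)], with √42 = 6.481 and z_power = 0.842.
- Chance of at least one false positive without correction, independent tests: 1 − 0.95^k.

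| Windows × scores | k | alpha/k | t | Critical \|r\| | Detectable \|r\| | 1 − 0.95^k |
|---|---|---|---|---|---|---|
| single test | 1 | 0.05 | 2.017 | 0.294 | 0.407 | 5% |
| 1 × 2 | 2 | 0.025 | 2.323 | 0.334 | 0.443 | 9.8% |
| 2 × 2 | 4 | 0.0125 | 2.607 | 0.369 | 0.474 | 18.5% |
| 3 × 2 | 6 | 0.00833 | 2.766 | 0.389 | 0.491 | 26.5% |

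Worked line for k = 4: 2.607 / √(43 + 6.80) = 0.369; tanh[(2.498 + 0.842) / 6.481] = 0.474.

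The tests would be correlated. In simulation, with correlations of 0 to 0.6 assumed among windows and among scores, the uncorrected figure is 15-19% for 4 tests and 20-27% for 6. With Bonferroni it is at most about 5% in either family. So carrying the Aim 1 correction across removes the excess, whichever of these families is used.

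**Step 4. Card-sort power**

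No figure is relied on. At the same assumed ability-sugar correlation of −0.40, two reasonable score models put the power of the 0-3 category (Spearman) at 0.36-0.41 and at 0.58-0.68. The documents give nothing that would choose between them.

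**The case for a change.** The best case for a change is that the fillings are not equivalent. An observed |r| of 0.38 passes with a family of 4 (0.369) and fails with a family of 6 (0.389). Section II.A presents the three separate periods as what makes the study unique, so a three-window analysis is a fair reading. The card-sort score is not chosen, and no pass mark is given for the border phase. A short paragraph would settle all this at no cost in visits or children, and it protects a reader only if it is written before the data are analysed.

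Much of this stands as description. The omission is plain, and writing the choices down early would be good practice. Three things limit it.

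- The 4-or-6 question arises in the same form for Aim 1, so it cannot be charged to the cognition aim.
- The card sort is run to a cited published procedure, which may supply the border pass mark. I cannot check that from the documents.
- The publication hope in V.D depends on more participants. The N of a cognition paper may not be 45, and the thresholds above would move with it.

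The significance sentence in V.B gives little help to either side. It follows a hypothesis about brain outcomes, so applying it to cognition is an inference.

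**Conclusion.** No change is called for. Section V.A is silent on Secondary Aim 1, but no stated number, rule or method is shown to give a wrong result. A competent analyst would correlate % calories in the two named periods with the PPVT-4 standard score and the 0-3 card-sort category, and would apply Bonferroni over the four tests or report estimates without a significance claim.

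The correction over four tests moves the critical |r| from 0.294 to 0.369 and the detectable |r| from 0.407 to 0.474. That is tolerable for a secondary aim in a pilot that promises no power. These figures assume N = 45, a two-sided 5% level and two windows by two scores. The conclusion would weaken if a later cognition paper reported selected windows or card-sort phases as confirmatory without saying how many had been examined.

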University of Kansas Medical Center
RESEARCH PROTOCOL INVOLVING HUMAN SUBJECTS
TEMPLATE WITH GUIDANCE

Version date: 2/19/2024

Principal Investigator: [name]

Study Title: Added sugar intake and brain structure and function

Co- Investigator(s): [name]

I. Purpose, Background and Rationale

A. Aim and Hypotheses

1. The first 1000 days post-conception have been characterized as a critical window for brain development, during which much of the brain's growth, structure, and function is set¹. Key nutrients from maternal and infant dietary intake fuels these maturational processes, thus providing the potential underlying foundation for later cognitive development. Brain growth and development is particularly sensitive to poor nutrition during this window²; previous work detailed the effects of deficiencies in the status of folic acid, choline, iron, zinc, iodine, and long chain polyunsaturated fatty acids³. While nutrient deficiencies have been studied, less is known about the impact and timing of excess nutrition in relation to cognitive development⁴.

2. Aim 1: Determine the relationship between added sugars (% calories) intake during pregnancy and infancy/toddlerhood (birth to 24 months) on brain structure and function.
Hypothesis: added sugars intake will be negatively related to brain structure (hippocampal volume) and function (resting state functional connectivity and P3 amplitude). We will explore how sex modifies this relationship.

Aim 2: Determine the relationship between fructose (% calories) consumption during pregnancy and infancy/toddlerhood (birth to 24 months) on brain structure and function. Since some studies reported relationships with fructose independently, we will explore relationships with fructose separately.

Hypothesis: fructose intake will be negatively related to brain structure (hippocampal volume) and function (resting state functional connectivity and P3 amplitude). We will explore how sex modifies this relationship.

B. Background and Significance

1. Study Significance: Brain development is a protracted process that begins in early gestation and continues into late adolescence. By the 8th week in gestation, the basic brain structures and the central nervous system are formed, and neuron production and migration are started⁵. From the 8th week until delivery, the cortical and subcortical structures form, including the major fiber pathways. In the third trimester, myelination

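### Both primary aims of this observational study are decided by correlations that include no covariate, and the sex modification promised under both aims has no analysis in Section V

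*Combined protocol and SAP*

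**What the plan says.** Section II.B states: "This is a non-interventional, observational study". Section II.D describes the children: "Inclusion criteria: Participated in ADORE GAINS. Age 5-6", and "Participants will be both male and female and English or Spanish speaking". The planned size in II.C is 45, described as a pilot.

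Section V.A opens with "The data analysis plan for each primary aim is described below". For Aim 1, V.A.1 says "we will examine the Pearson correlation between hippocampal brain volume and added sugars intake during pregnancy and infancy/toddlerhood". It gives Pearson correlations for functional connectivity and correlations for the P3 and N2 amplitudes, and ends with a Bonferroni correction whose number of tests is not given. For Aim 2, V.A.2 says "Correlations will be used to examine the relationship between brain measures and fructose consumption". V.B supplies the decision rule: "The strength of the correlations and level of significance will determine if there is a relationship between variables being tested".

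Neither V.A nor V.B names a covariate, a partial correlation, a regression model, a stratified analysis or an interaction.

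Section I.A adds to the hypothesis of each aim: "We will explore how sex modifies this relationship". The aims as restated in II.A leave this sentence out.

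**The concern.** There are two gaps.

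**No covariate.** The children differ in age within the 5-6 band and in sex. Any effect of either on a brain measure stays in the residual of an unadjusted correlation. If intake also differs systematically by age or sex, it enters the correlation itself. V.B then reads that correlation as the answer.

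**No sex analysis.** The sex question is part of both aims, and Section V presents itself as the plan for each primary aim. A team that follows Section V exactly cannot answer that question. A team that wants an answer must choose the method after seeing the data: separate correlations, a comparison of two correlations, or an interaction term.

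**Working it through.** The plan states no power, alpha or effect size, so there is no figure of its own to reproduce. The only input from the documents is n = 45 (II.C), taken here as 45 children with usable data. Everything marked *assumed* is illustration.

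**1. Cost of adjusting for age and sex**
- Pearson correlation: df = 45 - 2 = 43. With two covariates: df = 43 - 2 = 41.
- If the covariates explain nothing, the standard error grows by sqrt(43/41) = 1.024, or 2.4%.
- Break-even share of outcome variance: 1 - 41/43 = 4.7%.
- Critical correlation r = t/sqrt(t² + df) at an *assumed* two-sided 0.05: with t = 2.017 and 43 df, 0.294; with t = 2.020 and 41 df, 0.301.

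**2. Power gained** (simulation; *assumed* association -0.30, with age and sex unrelated to intake)

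| Variance explained by age and sex | Adjusted, 0.05 | Adjusted, 0.05/12 |
|---|---|---|
| 0% | 51% | 18% |
| 5% | 53% | 20% |
| 10% | 55% | 21% |
| 20% | 61% | 26% |

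Unadjusted power is about 53% and 19%. The divisor 12 is *assumed*: 3 hypothesised outcomes × 2 exposure windows × 2 sugars. The gain is small unless age and sex explain well over 5%.

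**3. When adjustment changes the error rate** (simulation; no true association; counting significant results in the hypothesised direction at 0.05, nominal 2.5%)
- Covariate independent of intake: the unadjusted test stays at about 2.5%, even when the covariate explains 20% of the outcome.
- Covariate *assumed* to explain 5-20% of the outcome and to be systematically correlated 0.1-0.3 with intake, in the direction that favours the hypothesis: 3.5-13.9% unadjusted, about 2.5% adjusted.

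Only the second case is a bias, and the documents do not show that it applies here.

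**4. Why a pooled correlation cannot show sex modification** (*assumed* split 22/23, with intake and outcome on the same standardised scale in both sexes)
- Slopes -0.3 and -0.3: the pooled value is -0.30.
- Slopes 0 and -0.6: (22 × 0 + 23 × -0.6)/45 = -0.31. The simulated mean is -0.304.

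The two situations give the same pooled result.

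**5. What a sex-by-intake term could deliver at n = 45**
- Rough form: half-width = t × s × sqrt(1/22 + 1/23), with t = 2.02 on 40 df (age in the model), s the residual SD, and the square root equal to 0.298. For s of 0.95-1.0 this gives 0.57-0.60.
- Simulated median half-width: 0.58-0.62 SD per SD of intake at 22/23, and 0.59-0.66 at an *assumed* 15/30.
- Power at 0.05 with a 22/23 split: 16% for slopes 0 against -0.3, and 53% for 0 against -0.6.
- Separate correlations are no more precise: r = -0.30 in 22 children has a Fisher-z 95% CI of -0.64 to 0.14.

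**The case against.** The strongest reply is that age and sex are weak candidates for confounding here. The exposures are maternal diet in pregnancy and child diet to 24 months; age at assessment is fixed years later by visit timing. Nothing in the documents links it, or the child's sex, to intake. What is left is mainly precision, where the gain is modest and may be a small loss. The sex question is only exploratory, is missing from the restated aims, and would be poorly estimated in a pilot of 45. All of this stands, and it limits the severity. It does not supply the missing sex analysis, and it does not make a 2.4% worst-case cost a reason to leave out two basic covariates.

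A reader might infer more than the documents support:
- *Chance imbalance in age or sex inflates false positives.* It does not. Chance imbalance is already part of the unadjusted test's error rate, as step 3 shows.
- *Sex analyses would produce many false positives.* The plan states a Bonferroni correction and does not exempt exploratory analyses. Twelve independent terms at 0.05/12 give 1 - (1 - 0.05/12)^12 = 4.9%.
- *Adjusting for age and sex deals with confounding.* It does little about whatever else goes with diet.
- *The decision rule is causal.* V.B speaks of a relationship. The language of effect in II.A and of public health recommendations in II.F stands outside the analysis rule.
- *Hippocampal volume is left uncorrected for head size.* The MRI methods are not in the text available, so this cannot be counted. They might also mention covariates, which lowers confidence somewhat, although Section V reads without gaps.

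**Conclusion.** The point holds on the text. Section V tests both primary aims with correlations that include no covariate, V.B makes those correlations the decision rule, and the sex question in both aims cannot be answered by any analysis that Section V describes.

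The second gap is the firmer one, because it is a mismatch within the plan and needs no assumption about effect sizes. The first is a cheap improvement, not a demonstrated bias: adjustment reduces bias only if age or sex is systematically related to intake. The degrees of freedom, the 2.4% and the 4.7% follow from n = 45. The power figures, the interval widths and the 12-test family rest on the assumptions stated with them.

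Severity is minor to moderate, given a pilot and an exploratory sex question.

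**What to change.** 1. In V.A.1 and V.A.2, relate each brain measure to intake by partial correlation or linear regression adjusted for age at assessment and sex. Report the unadjusted correlation alongside.
2. For hippocampal volume, connectivity and P3, add one exploratory sex-by-intake term per exposure. Report it as an estimate with a 95% CI, make no significance claim, and describe it as imprecise at n = 45.
3. Reword V.B so that the adjusted estimate and its interval carry the conclusion. State that it is an association and that confounders outside the model are not removed.

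This is plan wording only. Age is an eligibility criterion and both sexes are enrolled, so no new measurement is needed. The price is the two degrees of freedom, with a slight loss of precision if age and sex prove uninformative, and sex estimates too wide for a firm conclusion.
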